## 7. STUDY DESIGN

### 7.1 Summary of Study Design

This single-centre retrospective cohort study will use data derived from electronic patient records collected as part of routine patient care. It will be conducted at Portsmouth Hospitals University Trust NHS Trust, a large acute District General Hospital. Logistic regression and other classical statistical techniques will be used to predict the risk of death for different treatment methods and to identify clusters of patients with the same characteristics. This will allow identification of lower-risk treatment options for different patient groups.

### 7.2 Primary and Secondary Endpoints/Outcome Measures

The primary outcomes to be assessed will be length-of-stay, in-hospital, short-term (30-day), and long-term (1- year) mortality.

Secondary outcomes include: long-term complications, such as re-admission to hospital, additional abdominal surgery and the development of new medical conditions as well as the relationships between any of these outcomes and patient characteristics.

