The NoLap study does not provide information on the performance of laparoscopic (keyhole) procedures compared to laparotomies for abdominal emergencies. PHUT has championed the use of laparoscopy in emergency surgery, with progressive uptake by all consultants from 2014 onwards (11). By 2018, 60% of cases were completed laparoscopically, far higher than the national average of 8% (1). More importantly, this approach has been shown to be safe, with reduced mortality and length of stay (11). For patients unfit or unable to have any surgery, the Department of Interventional Radiology provides an on-call service to drain sepsis and embolise bleeds under local anaesthesia. In this study, information on the outcomes for patients who had an intestinal emergency managed laparoscopically or had an interventional radiology procedure will be collected. The effect of alternative treatments on patient outcomes will be assessed to determine which patient groups would most likely benefit from these interventions. This will benefit patients by providing clinicians with the scientific knowledge needed to develop better care pathways using these less invasive procedures. This will provide clinicians and their patients with the evidence they need to make a better-informed choice between laparotomy, minimally invasive procedures and symptomatic end of life care.

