### **8. SAMPLE SIZE**

This study will identify patients diagnosed with an intestinal emergency who may require surgery and observe patient outcomes, and how they correlate with the treatment they received. Trial analysis of all admissions in 2018 identified 901 patients with an abdominal emergency, 59% (530) of which had surgical intervention, either a laparotomy or a laparoscopy. Scaling these numbers to the study period of 6.5 years, we expect to identify a total of over 5,800 patients with an intestinal emergency and over 3,400 patients undergoing surgery. All UK hospitals have to submit data on all their intra-abdominal procedures to the National Emergency Laparotomy Audit (NELA). From previous analysis of PHUT NELA data (11), at least 30% of patients having an operation will have been completed laparoscopically. This is a remarkably large proportion of laparoscopic procedures compared to the UK average (8% according to NELA database) and will provide us over 1,000 laparoscopies in our study data set.

The PHUT data set includes a sufficient number of outcomes for model development (rule of thumb: 10 outcomes per predictor variable (25)). This study will be looking at a patient population with high mortality. Initial analysis of 2018 data identified in-hospital mortality as the rarest outcome with 23 deaths (4.3%) of patients having surgery and 28 deaths (7.6%) of patients not having surgery. Other outcomes occur in greater numbers. Collective numbers for the 6.5 year study period will therefore provide us with enough outcomes for the development of logistic regression models. The data set will be tested for separation and Firth's correction applied if necessary (26). Based on these numbers, we will be able to establish statistically significant correlations from this data set from a single hospital.

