### 10.2 Data analysis

Extracted data will be cleaned and quality controlled prior to analysis to ensure all relevant patients have been extracted. Given that our analysis will use only routinely collected, clinical data, missing values are unlikely to pose an issue. Initial analysis of 2018 data confirmed that clinical data within 24h of admission was almost fully complete for a remarkable >97% of admissions, meaning there is likely no need to impute data. We will test whether excluding admissions with missing data will introduce bias.

Our analysis can be broken down into the following steps:

- Comparison of the four treatment groups based on demographics, outcomes and medical pathway. This will include calculating mortality and long-term complication rates (Objective 2).
- Construct and compare risk models for each treatment group to predict short-term and long-term risk and to investigate the effect of both patient and hospital-level factors on outcome (Objective 3).

- Identify patients in each group who are abnormal for the group and might have fared better with a different treatment, using clustering algorithms (Objective 4).

After splitting the data set into subsets for each of the four patient groups using diagnosis and procedure codes (see above), mortality and long-term complication rates will be calculated for each group. Longer-term follow-up will include rates of re-admission to hospital, additional theatre visits and development of new medical conditions, within one year of initial admission with an abdominal emergency. Results will provide updated estimates of the average risks of different surgical procedures as well as the risk of not having surgery. Results will be compared with P-POSSUM mortality. Patient groups will further be characterised the using patient factors. Parameters of interest will include but are not limited to age, sex, mortality, long-term complication rates, admission early warning scores (NEWS, LDTEWS and LDTEWS:NEWS), frailty, medical history (previous ICD-10 codes).

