Patient group characteristics will be summarised with proportions for nominal and ordinal variables, means and standard deviations for continuous variables having symmetric unimodal distributions, and medians and interquartile ranges for other continuous variables. Clinical outcomes will be reported as proportions with 95% confidence intervals. Statistical tests of differences in proportions (Chi - nominal variables) and means/medians (ANOVA/Kruskal-Wallis) will be performed. Post-hoc pairwise comparisons will be carried out using Scheffe's method for ANOVA and Dunn's test for Kruskal-Wallis results and Bonferroni corrections for Chi results with significance at  $p < 0.05$ .

In the next step, we will identify which patient characteristics affect the outcome for a specific care pathway. Candidate predictor variables of 30-day mortality will be assessed with simple univariable linear regression and check for non-linearity. For each treatment group, we will construct a logistic regression model with the candidate predictor variables and non-linear terms as needed. Logistic regression performance will be tested using "goodness of fit" and discrimination. Goodness of fit, the ability to correctly predict risk, will be evaluated using the Hosmer-Lemeshow statistic (28) and by 10-fold cross-validation. Discrimination, the ability to rank cases in terms of risk, will be assessed using the Area Under the Receiver Operating Characteristic Curve (AUROC) (29). The relative importance of individual parameters will be assessed by the parameters Wald and t-statistics.

The last objective is to determine outlier clusters of patients who might have fared better on a different care pathway. For each treatment group, machine learning classification algorithms will be used to identify homogenous clusters of admissions in terms of their attributes. Each clustering will be reported by its method, number of clusters and intracluster correlation coefficients (ICCs) with 95% confidence intervals and used to extend the logistic regression risk model for the treatment group to see if the model is improved as measured by a likelihood ratio test. Where this is the case the patient subgroups corresponding to the clusters will be analysed in terms of their clinical characteristics.

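### In-hospital mortality, a co-primary outcome without a time window, is compared across treatment groups whose stays are expected to differ, so earlier discharge can lower the observed figure at the same underlying risk

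*Protocol*

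**What the plan says.** Protocol section 7.2 lists the primary outcomes: "The primary outcomes to be assessed will be length-of-stay, in-hospital, short-term (30-day), and long-term (1- year) mortality". Section 10.1 repeats the list. Neither place gives in-hospital mortality a time limit.

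Section 10.2 sets out how outcomes are used. The first analysis step is "Comparison of the four treatment groups based on demographics, outcomes and medical pathway". On reporting it says: "Clinical outcomes will be reported as proportions with 95% confidence intervals". Differences in proportions are tested by chi-squared, with Bonferroni-corrected pairwise comparisons at 0.05. Nothing in this section takes account of time spent in hospital.

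The protocol expects stay to vary with treatment. Of laparoscopy, section 4.2 says "this approach has been shown to be safe, with reduced mortality and length of stay", and length of stay is itself one of the primary outcomes.

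Section 9.1 obtains 30-day and 1-year mortality from linked data. Section 10.2 names 30-day mortality as the outcome against which candidate predictors are assessed. Section 8 gives 2018 counts for in-hospital deaths only: "Initial analysis of 2018 data identified in-hospital mortality as the rarest outcome with 23 deaths (4.3%) of patients having surgery". For the group managed without an operation it gives a count of 28, or 7.6%.

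**The concern.** A death counts as in-hospital only if it comes before discharge. Each patient is therefore watched for as long as he or she stays, and stay is something the treatment may change. Two groups with the same course of risk but different stays would show different in-hospital mortality, and an unadjusted comparison of proportions would attribute the difference to treatment.

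The comparison most exposed is laparoscopy against laparotomy. Section 4.2 gives laparoscopy the shorter stay, and section 4.4 expects the results to support wider use of laparoscopy nationally. A bias towards the shorter-stay group would run in the direction of that conclusion.

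Section 8 suggests that truncation at discharge does occur. It calls in-hospital death the rarest outcome and says the others are more frequent. If that ranking includes 30-day mortality, some deaths within 30 days must have happened after discharge.

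**Working it through.** **1. The plan's own figures.** From section 8: "Trial analysis of all admissions in 2018 identified 901 patients with an abdominal emergency, 59% (530) of which had surgical intervention".
- Surgery: 23/530 = 4.34% (stated 4.3%).
- No surgery: 901 − 530 = 371; 28/371 = 7.55%, against 7.6% stated, a trivial difference.
- Over 6.5 years: 901 × 6.5 = 5,857 patients and 530 × 6.5 = 3,445 operations. At 30% laparoscopic, 0.30 × 3,445 ≈ 1,033, which leaves 2,412 laparotomies.

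These agree with the plan's projections. The plan gives no stay by group and no 30-day count, so the bias cannot be computed from it, only illustrated.

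**2. Inputs to the illustration.**
- 30-day mortality of 10% in both groups. This is the national laparotomy figure in section 4.2; equality between groups is imposed so that any difference comes from stay alone.
- Stays of 5 v 12 days and 7 v 14 days: assumptions.
- The same death process before and after discharge, with every patient in a group having the same stay: assumptions.

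In-hospital mortality for stay L is 1 − exp(−H(L)), where H is the cumulative hazard and H(30) = −ln(0.90) = 0.10536.

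**3. Constant hazard.** h = 0.10536/30 = 0.003512 per day.
- L = 5: 1 − exp(−0.01756) = 1.7%
- L = 12: 1 − exp(−0.04214) = 4.1%
- Ratio about 2.4; both groups have 10% at day 30.

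**4. Early-peaking hazard (Weibull, shape 0.5).** H(L) = λ√L, with λ = 0.10536/√30 = 0.01924.
- L = 5: 1 − exp(−0.04301) = 4.2%
- L = 12: 1 − exp(−0.06664) = 6.4%
- Ratio about 1.5; again 10% in both groups at day 30.

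**5. Range over assumed stays, 30-day mortality 10% throughout.**

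| Stay (days) | Constant hazard | Early-peaking |
|---|---|---|
| 5 | 1.7% | 4.2% |
| 7 | 2.4% | 5.0% |
| 10 | 3.5% | 5.9% |
| 12 | 4.1% | 6.4% |
| 14 | 4.8% | 6.9% |
| 20 | 6.8% | 8.2% |

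**6. Could a test pick this up?** Take 1,033 laparoscopies and 2,412 laparotomies, a two-sided 0.05 level before Bonferroni, and this pair alone. For 7 v 14 days under constant hazard, the difference is 0.02369, its standard error under no difference is 0.00736, and its standard error under the stated rates is 0.00647. Then (0.02369 − 1.96 × 0.00736)/0.00647 = 1.43, a probability of 92%. Under the early-peaking hazard it is 60%. For 7 v 10 days the figures are 34% and 19%. With equal 30-day risk, a sound test would reject in 5%.

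**The case against.** The case against has force on several points.

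- **Fixed-window outcomes are already there.** 30-day and 1-year mortality are primary in the same sentence, come from linked data, and will be reported beside in-hospital mortality and length of stay. A reader might infer that the whole treatment comparison, or the risk models, are biased. The documents do not support that: 30-day mortality is the outcome named for the model predictors, and no section rests a conclusion on in-hospital death alone. This limits the reach of the point. It does not remove an outcome that is primary and is to be compared between groups.
- **Section 8.** Because in-hospital mortality is the only one with counts, a reader might infer that the plan favours it for comparing treatments. It does not. For a check of events per predictor, the rarest outcome is the conservative choice, and section 8 gives that reason. This objection stands in full.
- **Size.** A reader might take the 2.4-fold ratio as the size of the bias. It is one constant-hazard scenario; an early-peaking hazard gives about 1.5 for the same stays. If patients judged at risk are kept in, the gap shrinks further. This stands.
- **Direction.** Death also shortens stay, so a short-stay group need not look better. The shorter stay after laparoscopy rests on one cited series, with no size given. A reader might also infer that end-of-life patients leave hospital to die elsewhere; the protocol gives neither place of death nor discharge destination, so that is only an assumption. What stands is conditional: at equal underlying risk, earlier discharge lowers the observed in-hospital figure.

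A statistical analysis plan might add an allowance for time at risk, but the choice of a discharge-ended primary outcome is made in the protocol.

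**Conclusion.** The point holds for the between-group comparison of in-hospital mortality. That outcome is co-primary, has no window, and is to be compared as an unadjusted proportion between groups whose stays the protocol expects to differ. Earlier discharge can lower the observed in-hospital mortality of a group; it says nothing about that group's true mortality.

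The size is not known. The figures above rest on assumed stays, an assumed hazard shape, equal 30-day mortality of 10%, and discharge unrelated to prognosis. They show that the effect could be large enough to matter, not that it will be. Because two fixed-window mortality outcomes are already primary, this is a moderate fault in one comparison and does not threaten the main risk estimates.

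**What to change.** In sections 7.2 and 10.1, state that between-group mortality tests use 30-day mortality (short-term) and 1-year mortality (long-term), both counted from admission. Keep in-hospital mortality as a descriptive result, shown for each group beside length of stay and, if held, discharge destination.

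The cost is wording only, since section 9.1 already supplies both fixed-window outcomes; no new data or change of cohort is needed. The downside is that in-hospital deaths after day 30 would enter a between-group test only through the 1-year figure. Section 8 needs no change for this point.

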### 7.3 Study Setting

This single-centre retrospective cohort study will use data derived from electronic patient records collected as part of routine patient care. It will be conducted at Portsmouth Hospitals NHS Trust (PHUT), a large acute District General Hospital. Logistic regression and other classical statistical techniques will be used to predict the risk of death for different treatment methods and to identify clusters of patients with the same characteristics. This will allow us to identify lower-risk treatment options for different patient groups.

Portsmouth hospital provides acute services to a population of about 860,000 people, covering a mix of rural, urban and coastal areas. Portsmouth is the most densely populated city in the UK. Interspersed with areas that attract well-educated professional families and wealthy retired residents, Portsmouth has several areas of 'multiple deprivation' and it's in the top 20% of areas in England for deprivation (deprivation index 27.1, England average 21.8) (23). It's a very diverse city with a large student and military service population as well as a high number of elderly people in their 80s and 90s. In 2015-2016, PHUT was placed 120 out of 135 acute trusts in England, according to the standardised hospital mortality index (SHMI) (24). Preliminary analysis using the [name] Intelligence Portal showed that mortality of patients with abdominal emergencies admitted

to Portsmouth Hospital Trust in 2018 was in line with the national average. In other words, Portsmouth is a representative microcosm of the UK in terms of its demographic profile and hospital performance. PHUT is, however, exceptional as it performs an unusually large proportion of laparoscopic procedures every year making it ideally suited for this study.

#### **7.4 Study cohort**

Data will be derived from electronic patient records collected as part of routine clinical patient care on all general adult wards (excluding maternity) between 2013 (beginning of NELA and collection of data of interest) and 2020.

All patients with a condition that would qualify them for emergency abdominal surgery will be identified, using their ICD-10 diagnosis and OPSC-4 procedure codes which are part of the electronic patient record. Once patients have been identified, they will be screened against the inclusion/exclusion criteria (see below). For each patient, this will include only the first intervention within the study period in the analysis. Subsequent admissions with an abdominal condition or subsequent interventions will be classified as complication and therefore considered as an outcome.

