## 4. BACKGROUND AND RATIONALE

### 4.1 What is the problem being addressed?

30,000 emergency abdominal laparotomies are performed each year in England and Wales (1). Each involves making a large incision down the middle of the abdomen to gain access to the abdominal cavity. In 2011, the Royal College of Surgeons England issued a report highlighting concerns that the mortality rate for patients having laparotomy was about twice that of open-heart surgery, with a number of shortfalls in patient care contributing to this (2, 3). Since 2013, the National Emergency Laparotomy Audit (NELA) has monitored outcomes from emergency laparotomy across the UK. The audit sets standards of care against which hospitals are benchmarked, such as early administration of antibiotics, CT-scan for diagnosis, pre-operative risk assessment, consultant surgeon/anaesthetist presence in theatre and transfer to intensive care postoperatively, leading to better outcomes (1, 4-6).

Conversely, patients with intestinal emergencies who do NOT have a laparotomy are not well characterised and do not receive the prioritised care that patients having surgery do; even though their condition is no less severe. There is a significant lack of information on the outcome and quality of life of patients who do not have a laparotomy. In the UK, only a single small study, the NoLap Study (7), has looked at this. They found a 30-day mortality of 63% in these patients compared to 13% for those who had a laparotomy. It is this surprisingly large group of patients (32%), who have such a poor outcome that deserves further investigation.

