### 4.2 Why is this important?

Patients who do have a laparotomy are high risk, with a 10% mortality rate at 30 days measured nationally. This group is closely scrutinised by the National Emergency Laparotomy Audit (NELA) who set strict standards of care, and outcomes from surgery are well characterised (1, 2, 4-6). However, there is clear evidence that patients with intestinal emergencies who do NOT have emergency abdominal surgery (laparotomy) do very poorly, with only 30% of patients surviving to a year from admission (7). Our concern is that patients not undergoing laparotomy, but with the same life-threatening pathology, are being forgotten and do not receive the focus of care that they deserve. To improve the quality of care for these patients, better understand the risk of mortality and associated patient factors for ALL patients admitted with an intestinal emergency is needed.

This much-needed study will benefit patients by providing information on the 30-day and 1-year mortality for all patients with an intestinal emergency admitted to our hospital over a 6.5-year period. By observing relationships between mortality and patient factors like age, diagnosis, co-morbidities, vital signs, blood tests and surgery versus no-surgery, factors influencing patient outcomes will be identified and better understood. The "NoLap" study (7) suggested that a cohort of these patients who didn't have a laparotomy might in retrospect have had a better chance of survival if they had. To investigate this, patient factors will be analysed and patterns that significantly influence mortality will be determined. Results will provide insights into the different patient groups and improve our

understanding of their risk of death, with or without surgery. This will enable clinicians to more intelligently advise patients and their relatives on risks of laparotomy against alternative management.

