### 5. PRELIMINARY STUDIES AND EXPERIENCE OF INVESTIGATORS

This study is a continuation of a long-standing collaboration between the University of Portsmouth (UoP) and Portsmouth Hospitals NHS Trust (PHU). The team has 20 years of experience in extracting and linking these types of data sets for work in clinical outcome modelling and risk prediction.

Our work has previously led to the development of VitalPAC, P-POSSUM (Portsmouth Physiological and Operative Severity Score for the enUmeration of Mortality and morbidity) (18) and ViEWS. NEWS was a minor modification of ViEWS and its latest version (NEWS2) is now mandated for use in NHS hospitals and ambulance trusts (37,22). P-POSSUM, although initially developed as an audit tool, was recommended for use by the Royal College of Surgeons in 2011 as pre-operative risk prediction tool (2). They quote:- "P-POSSUM, freely available on the internet, is possibly the simplest and best-validated method" and: "The POSSUM score is the most validated risk prediction method for general and vascular patients that takes into account pre-operative and peri-operative factors. P-POSSUM may be used for all patients. A predicted mortality risk  $\geq 10\%$  indicates a need for critical care admission, except for patients on end-of-life pathways with appropriate palliative care facilities available at ward level."

Importantly, this team has a track record and ongoing studies of the outcomes of major abdominal surgery and less-invasive approaches, as evidenced by these 2 recent publications in peer reviewed journal:

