## 9. DATA HANDLING AND RECORD KEEPING

### 9.1 Data collection and extraction

Data will be derived from electronic patient records collected as part of routine clinical patient care on all general adult wards (excluding maternity) between 2013 (beginning of NELA and collection of data of interest) and 2020. Electronic records will include patient demographics, diagnosis and procedure codes held on the Patient Administration System (PAS), vital sign observations from the Vitalpac™ system, routine blood tests from the pathology database, surgery-specific data from TheatreMan™ and additional data from the National Emergency Laparotomy Audit (NELA; which is only available for patients who underwent laparotomy). Linked data sets will provide information on length-of-stay in-hospital mortality, 30-day mortality, 1-year mortality, re-admission to hospital and subsequent abdominal surgery.

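### The cohort is scoped to general adult wards, which is narrower than the all-patients aim and may leave out deaths that occurred without a ward stay

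*Protocol*

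**What the plan says.** **Source of the cohort.** Section 7.4 begins: "Data will be derived from electronic patient records collected as part of routine clinical patient care on all general adult wards (excluding maternity". Section 9.1 repeats that the records are those "collected as part of routine clinical patient care on all general adult wards (excluding maternity", and the participants row of the Synopsis has the same sentence. None of the three names the emergency department or critical care as a source, or says how a patient with no general-ward stay is handled.

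**Identification and data sources.** The next paragraph of Section 7.4 continues: "All patients with a condition that would qualify them for emergency abdominal surgery will be identified, using their ICD-10 diagnosis and OPSC-4 procedure codes". Section 9.1 lists "diagnosis and procedure codes held on the Patient Administration System (PAS), vital sign observations from the Vitalpac™ system", then the pathology database, TheatreMan and NELA. It notes that NELA covers laparotomy patients only.

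**Aim and planning numbers.** Section 4.2 promises 30-day and 1-year mortality for "all patients with an intestinal emergency admitted to our hospital over a 6.5-year period". Objective 1 in Section 6.2 likewise covers every qualifying patient, operated or not. Section 8 starts from this: "Trial analysis of all admissions in 2018 identified 901 patients with an abdominal emergency".

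**Criteria and checks.** The inclusion criteria require one full set of vital signs and one of routine blood tests on the day of admission, without saying where they must be recorded. No criterion requires a ward stay. Section 10.2 reports that 24-hour data were almost fully complete for more than 97% of 2018 admissions, and plans a check for bias from excluding admissions with missing data.

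**The concern.** The ward sentence reads as a scope rule. It opens the section that defines the cohort, and its parenthesis removes a population. As a scope rule it is narrower than the aim and narrower than the run behind the planning numbers.

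The patients at risk of being missed are those who never reach a general ward, because they die in the emergency department, in theatre or in critical care. A similar patient who survives to step down to a ward would be included. Entry would then depend partly on surviving the early period, and observed mortality would be too low. Mortality by treatment group is the primary endpoint in the Synopsis. In-hospital, 30-day and 1-year mortality are all primary outcomes in Section 7.2, and an early death left out of the cohort is missing from all three.

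**Working it through.** **1. Reproduce the plan's own figures (Section 8).**
- Expected patients: 901 × 6.5 = 5,856.5 (stated: over 5,800).
- Expected operated patients: 530 × 6.5 = 3,445 (stated: over 3,400).
- Not operated in 2018: 901 − 530 = 371.
- In-hospital mortality: 23/530 = 4.34% (stated 4.3%) and 28/371 = 7.55% (stated 7.6%, a rounding-level difference).

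The planning numbers therefore rest on all admissions. If the real extraction follows the ward wording and that is narrower, the expected numbers do not describe the cohort that will be extracted.

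**2. Set the statements side by side.**

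| Place | Population |
|---|---|
| Synopsis, 7.4 (opening), 9.1 (opening) | Records from general adult wards, maternity excluded |
| 4.2; 6.2 Objective 1; 7.4 (second paragraph) | Every patient with a qualifying emergency |
| 8 | All admissions in 2018 |
| 7.4 criteria | No ward-stay rule, but full day-of-admission vital signs and bloods |

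The first row can be read as a limit on the others or as loose description. The protocol does not say which.

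**3. Could the listed sources find a patient with no ward stay?** An operated patient could be found through PAS or TheatreMan, and a laparotomy patient also through NELA. A non-operated patient depends on PAS. Any of them must still have a full set of vital signs on the day of admission. Vitalpac is the only vital-sign source named, and the protocol does not say whether it covers the emergency department, theatre or critical care. Widening the frame alone may therefore not bring these patients in.

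**4. Does the completeness figure settle it?** No. It was measured among admissions already identified, and almost fully complete is not the same as a full set. If it refers to the 901 patients (an assumption), up to 3% × 901 = 27 could have incomplete data. That is not small beside 23 + 28 = 51 deaths.

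**5. Scale, under assumed losses.** The protocol gives no count of deaths without a ward stay. Take the 2018 counts as complete and suppose k deaths in a group are left out, so that mortality = (d − k)/(n − k).

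| k | Operated (d = 23, n = 530) | Not operated (d = 28, n = 371) |
|---|---|---|
| 0 | 4.34% | 7.55% |
| 2 | 21/528 = 3.98% | 26/369 = 7.05% |
| 5 | 18/525 = 3.43% | 23/366 = 6.28% |
| 10 | 13/520 = 2.50% | 18/361 = 4.99% |

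The columns are separate illustrations. For equal k, the non-operated rate falls by more percentage points (at k = 5, 1.26 against 0.91).

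**6. Direction between groups.** Suppose instead that a share x of deaths is lost, so that mortality = d(1 − x)/(n − dx). The observed ratio of non-operated to operated mortality is 7.55/4.34 = 1.74.
- 20% lost in both groups: 18.4/525.4 = 3.50% and 22.4/365.4 = 6.13%, ratio 1.75.
- 40% lost in both groups: 13.8/520.8 = 2.65% and 16.8/359.8 = 4.67%, ratio 1.76.
- 20% of operated and 40% of non-operated deaths lost: 4.67/3.50, ratio 1.33.

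The direction is set by the assumed split, which the protocol does not give.

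**The case against.** The strongest reply is that the ward sentence only describes adult, non-maternity inpatients. The paragraph after it identifies every qualifying patient from codes, the criteria contain no ward-stay rule, and PAS, TheatreMan and NELA are not ward records. On this reading, the all-patients aim and the 2018 run show what the authors meant.

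Much of that stands. Exclusion is possible, not certain, and nothing says that deaths outside a general ward are removed. But the reply does not remove the ambiguity. In Section 9.1 the list of sources follows the ward sentence and can be read as itemising those ward records. Two data managers could build different queries from the same text. The check in Section 10.2 concerns admissions with missing data, so patients outside the frame would not appear in it.

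A reader might go further and infer that surgical mortality is lowered most, since the protocol links surgery with critical care. Section 4.1 mentions "transfer to intensive care postoperatively", and Section 5 cites a predicted risk that "indicates a need for critical care admission, except for patients on end-of-life pathways with appropriate palliative care facilities available at ward level". The documents do not support that step. The first is an audit standard and the second comes from a college report; neither describes patient flow at this Trust. A patient who dies in the emergency department before any operation counts as non-operated. An operated patient with a ward stay before surgery stays in the frame. Surgery comes out as the group affected most only if few or no non-operated deaths are assumed lost.

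**Conclusion.** The point holds as an inconsistency in the cohort definition. Three places scope the records to general adult wards, while the aim, Objective 1 and the planning run cover all patients or all admissions. Read literally, the ward wording may omit early deaths and so lower observed mortality.

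Neither the number of such deaths nor their division between treatment groups is in the documents. The size of the effect is therefore unknown, and the direction of any bias between groups must be left open. The illustrative losses assume that the 2018 counts are complete. They show only that, with 23 and 28 in-hospital deaths a year, a handful of omitted deaths would visibly move a group's rate.

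**What to change.** 1. In the Synopsis, Section 7.4 and Section 9.1, define the frame as all adult non-maternity admissions to the Trust regardless of location (emergency department, theatre, critical care or ward), identified from PAS, TheatreMan and NELA codes. Say whether a death in the emergency department before formal admission counts.
2. In the inclusion criteria, state that the day-of-admission vital signs and blood tests may come from any location. In Section 9.1, name the source of vital signs for patients not covered by Vitalpac.
3. In Section 10.2, extend the bias check to patients with no general-ward stay.
4. Report by treatment group the number of patients and deaths with no general-ward stay, and the number of patients and deaths excluded for lack of day-of-admission data.

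The cost is protocol wording and a wider query, mostly on systems already being extracted. Some added patients will have less complete observations, and a further vital-sign source may be needed if Vitalpac does not cover every location.
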